134 degludec from the subcutaneous injection site into the circulation [8-10]. This is the major
135 difference with insulin glargine which, following subcutaneous injection, forms microprecipitates
136 that must re-dissolve prior to absorption and which renders its absorption inherently variable [8-
137 10].

138 The longer duration of action and the lower day-to-day insulin degludec variability makes it an
139 appealing choice when patients want to start multiple daily injections. In addition, when compared
140 to insulin glargine, insulin degludec is associated with lower incidence of nocturnal and overall
141 hypoglycemia in insulin requiring patients with diabetes [11].

142 However, differently from insulin glargine, the time needed from first dose of insulin degludec to
143 reach steady state, defined as serum concentration exceeding 90% of the final plateau, is about 2 to
144 3 days, being at 60% of steady state within at day 1 and 85% at day 2 [12-13]. This results in an
145 increased risk of hyperglycemia, during the initial 48-72 hours of CSII to MDI transition using
146 insulin degludec.

147 Current CSII to MDI transition strategy is to stop CSII and initiate long acting insulin (such as
148 glargine or detemir 1:1) from day 1 of stopping insulin pump [14-17]. However, the standard of
149 care strategy has not been successful at the Barbara Davis Center for Diabetes, a leading T1D
150 center in the world (unpublished observation), due to significant hyperglycemia during the first 48-
151 72 hours of this transition. Hyperglycemia for initial 2-3 days makes transition from CSII to MDI
152 difficult and frustrating for the patients. Therefore, there is a need to have a standardized approach
153 to transitioning patients from CSII to MDI using insulin degludec.

154 Considering the lack of evidence and knowledge gap, this study is proposed to examine an
155 investigational approach in contrast to the clinical standard of 1:1 dose conversion in an attempt to
156 lower the incidence and/or duration of hyperglycemia after transition from insulin pump.

157 **2. SPECIFIC OBJECTIVES:**

158 The primary objective of this study is to evaluate the efficacy and safety of an alternative CSII to
159 MDI transition strategy using insulin degludec compared to the standard of care in adults with
160 T1D.

161 **3. RESEARCH DESIGN AND METHODS:**

162 **3.1. Study Hypothesis**

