- 199 ○ Randomization phase (Week 1 to week 2): Subjects will be randomly allocated to one of
- 200 two transition protocols (1:1 randomization).
- 201 ○ Follow-up phase (Week 2 to week 3): Subjects will return to their preclinical trial CSII
- 202 regimen.

203 **Figure 1:** Study Design
 204

205 **3.4. Rationale for study design**

206 The rationale behind the overlap protocol strategy is linked to insulin degludec pharmacokinetic
207 and pharmacodynamics. Indeed, insulin degludec steady state concentration reaches 60% and 85%
208 respectively at day 1 and 2, and 100% steady state is reached on day 3 from the first day of insulin
209 degludec injection [12-13].

210 Therefore, 50% and 75% dose reduction proposed in the overlap transition strategy of the first 2
211 days will cover for the slow rise of insulin degludec concentration the first 2 days, and the 100%
212 insulin pump discontinuation on day 3 will correspond to the time needed for insulin degludec to
213 reach the steady state. This would reduce time spent in hyperglycemia post-CSII discontinuation.

214 Rationale for blinded CGM: Since the primary outcome is time spent in hyperglycemia (CGM
215 glucose >180 mg/dl), it is necessary to have CGM during randomized phase. Real-time CGM
216 would interfere with the primary and secondary outcomes as patients will have ability to see CGM
217 glucose trend and adjust insulin accordingly. Therefore, blinded CGM would be appropriate for
218 this research protocol. In addition, the time in range (and percentage of hypoglycemia) also
219 depends on person' ability to manage diabetes and therefore, baseline CGM will provide the data
220 about time-in-range and time spent in hyper-and hypo-glycemia. The information from blinded
221 CGM during run-in-phase will be useful for analysis of primary and secondary outcomes that will
222 be adjusted for baseline CGM glucose metrics. Blood glucose fluctuations are greatest during the
223 first week of insulin pump to MDI transition and therefore, 1 week CGM period is enough for
224 comparison of primary and secondary outcomes between the groups.

225 **4. CLINICAL RESEARCH SITES**

226 The study will be conducted at a single site, Barbara Davis Center for Diabetes.

227

228 **5. STUDY POPULATION:**

229 We plan to enroll 34 participants with the expectation that 30 will be randomized and complete the
230 study.

231 **5.1. Inclusion criteria**

232

233 1) Age ≥ 18 years and ≤ 65 years

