- 400 and will start insulin degludec injection (1:1 dose conversion) once a day in the
- 401 morning.

402 ○ Group 2 (overlap transition): Subjects will receive insulin degludec in full dose (1:1
 403 dose conversion) at randomization, and CSII basal rate will be reduced by 50%
 404 during the first 24 hours of the transition and by 75% during 24 to 48 hours of the
 405 transition. CSII will be discontinued on day 3 of the transition.

406 The insulin degludec initiation and CSII basal reduction over 72 hours has been summarized in
 407 Table 2;

408 **Table 2:** CSII changes and MDI initiation by randomization groups
 409

Randomization	Treatment Change	V2 (Day 7±1)	P1 (V2+24 hours)	P2 (P1+24 hours)
Group 1(n=15) Standard of care	CSII	Discontinuation		
	Insulin degludec	Once a day in the morning (1:1 dose conversion)		
	Insulin aspart	Based on carbohydrate ratio and correction factor		
Group 2(n= 15) Overlap transition	CSII	50% basal rate reduction	75% basal rate reduction	Discontinuation
	Insulin degludec	Once a day in the morning (1:1 dose conversion)		
	Insulin aspart	No insulin aspart injections as patients will be using boluses through insulin pump	No insulin aspart injections as patients will be using boluses through insulin pump	Insulin aspart injections based on carbohydrate ratio and correction factor

410

411 ○ Insulin degludec dose conversion guidance:

412 • On the day of randomization, CSII will be downloaded and information on average basal
 413 insulin for the last 3 days, carbohydrate ratio and correction factor will be recorded.

414 • The average basal insulin for last 3 days will be used to calculate insulin degludec U-100
 415 starting dose. For example; average basal insulin during last 3 days of CSII is 20 units/day,
 416 the insulin degludec U-100 starting dose will be 20 units/day. The dose will be rounded up or
 417 down as needed. E.g. if patient’s total daily dose is 32.4 units, it will be rounded to 32 units

418 per day. All subjects will be instructed to use insulin degludec once a day in morning only.
419 The first dose of insulin degludec will be given in the clinics at Visit 2.

- 420 • The dose of insulin aspart will be based on patient’s own carbohydrate ratio and correction
421 factor. Carbohydrate ratio is defined as the number of carbohydrates covered by each unit of
422 rapid acting insulin. Correction factor (aka insulin sensitivity factor) is defined as how much

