423 one unit of rapid acting insulin will drop blood glucose. For example; a patient with
424 carbohydrate ratio of 1:15 and correction factor of 1:50 >150 will take 3 units if preprandial
425 blood glucose is ~200 mg/dl for 30 grams of meal (2 units for 30 grams of carbs + 1 unit for
426 correction). Subjects randomized to group 2 will be instructed to start insulin aspart 48 hours
427 after randomization; i.e. when they disconnect their insulin pump.
- 428 ▪ It is likely that patients randomized to standard-of-care group may experience
429 hyperglycemia during first 48-72 hours. Therefore, both groups will be given a diary
430 (**Appendix 1**) to record any correction made during the randomization phase to count extra
431 insulin injections needed to correct blood glucose during first 72 hours.

432 **6.4. Phone call 1 [P1, week 2, visit 2+24hrs] and phone call 2 [P2, week 2, P1+24hrs]**

- 433 ▪ As a safety measures, there will be 2 phone calls 24 and 48 hours after randomization,
434 respectively.
- 435 ▪ Phone call 1 (P1) will be done 24 hours (± 6 hours in case if patient does not respond to first
436 phone call) after visit 2.
- 437 ▪ Phone call 2 (P2) will be done 24 hours (± 6 hours in case if patient does not respond to first
438 phone call) after P1.
- 439 ▪ All subjects will be asked/assessed for

- 440 ○ Any episodes of severe hyperglycemia requiring hospitalization or hypoglycemia
- 441 requiring third person' assistance. These events will be recorded as SAE and insulin
- 442 dose modification will be done at discretion of the investigator for safety reasons.
- 443 ○ Correct insulin dose and administration will be reassessed.
- 444 ○ Maintenance of glucose and insulin injection dairy.
- 445 ○ Any skin reaction at CGM site.
- 446 ■ For Group 2 (overlap transition):
- 447 ○ Instructions to change in basal rate (75% basal reduction) will be done at P1
- 448 ○ Instructions for CSII discontinuation and initiation of insulin aspart based on
- 449 carbohydrate ratio and correction factor at P2

450 **6.5. Visit 3, week 2, day 14±1: end of treatment**

- 451 ■ Blood glucose meter download and review of SMBG.
- 452 ■ Subject's blinded CGM will be removed and downloaded.
- 453 ■ Look for any local skin reaction at the site of CGM insertion.
- 454 ■ Subjects will return all the remained study-related products (CGM device components,
- 455 insulin degludec and aspart pens, and any auxiliary supplies)
- 456 ■ Report any AE/SAE if any.

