- 457 ■ Subjects will be transitioned back to their preclinical trial insulin pump regimen. The same
- 458 basal and bolus settings will be used as of preclinical trial insulin pump settings. However,
- 459 there may be changes made to basal and bolus insulin doses depending on blood glucose
- 460 control during the study period at the discretion of investigators. To reduce the risk of

461 hypoglycemia, subjects will be advised to set a 50% temporary basal insulin rate for 24 hrs
462 following insulin degludec transition.

463 **6.6. Phone call 3, week 3, day 21±1: follow-up phone call and end of the study**

464 ▪ The intention of phone call 3 is to make sure that subjects are not experiencing major
465 hypoglycemia or hyperglycemia events. The study coordinator will make a phone call to
466 assist subjects if they require insulin dose adjustments. AE/ SAE will be recorded, if any,
467 during third week of clinical trial. However, they would not be a part of statistical analysis.

468

469

470

471

472

473

474

475

476

477

478

479

480

481

482

483 **6.7. Table 4: study visit outline**

Period	Screening and Run-In-Phase	Randomization			End of treatment	Follow-up
		V1	V2	P1		
Visits	V1	V2	P1	P2	V3	P3
Day/time from last visit	0	7	V2 + 24hrs	P1 +24hrs	14	21
Time window		±1 day	±6hrs	±6 hrs	±1 day	±1 day
Subject related info/assessment						
Informed consent	X					
Inclusion/exclusion criteria	X					
Screen fail/withdrawal criteria	X	X				
Demography and medical history	X					
Diabetes history	X					
GOLD questionnaire	X					
IDSS, and WPAI questionnaire	X	X			X	
Concomitant illnesses	X					
Review of current medications	X					
Vital signs	X					
BMI	X					
Physical examination	X					
Report AE/SAE	X	X	X	X	X	X
Trial material/steps						
Dispensation of study drugs	X	X				
SMBG and DSM education	X					
Glucose and insulin diary		X	X	X		
Blinded CGM insertion/training	X	X				
Blinded CGM removal/download		X			X	
SMBG profile	X	X				
MDI initiation and training		X				
Randomization		X				
Transition back to CSII					X	
Compliance check		X				
Blood Draw						
POC A1c, urine pregnancy test*	X				X	
CMP (blood sampling)	X					

484 V1, V2, V3 stand respectively for visit 1, 2 3; P1, P2, P3 stand respectively for phone call 1, 2, 3
485 SMBG; self-monitoring of blood glucose, BMI; body mass index, DSM; diabetes self-
486 management education, POC; point-of-care.
487 *pregnancy test only for women in reproductive age.

488
489

490

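### Return to the pump at Visit 3: the last degludec dose is not stated and no contact is scheduled until day 21±1; a cheap participant-safety improvement

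*Combined protocol and SAP*

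**What the plan says.** **Daily dosing.** The dose conversion guidance in section 6.3 sets degludec at 1:1 with the average pump basal of the last 3 days and gives the standing instruction: "per day. All subjects will be instructed to use insulin degludec once a day in morning only". Neither 6.3, 6.4 nor 6.5 names the last dose or makes an exception for the Visit 3 morning.

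**Return to the pump.** Section 6.5 (day 14±1, end of treatment) has participants hand back their pens and resume their pre-trial pump settings, which the investigator may change in the light of glucose control during the study. The written precaution against low glucose is: "hypoglycemia, subjects will be advised to set a 50% temporary basal insulin rate for 24 hrs". At the same visit the meter readings are reviewed, and "Subject's blinded CGM will be removed and downloaded".

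**Contact afterwards.** Section 6.6 and Table 4 list one further contact, on day 21±1: "The intention of phone call 3 is to make sure that subjects are not experiencing major" hypo- or hyperglycemia events. On the way into injections, section 6.4 schedules safety calls to all participants at 24 and 48 h.

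**Degludec kinetics.** The background says the time to "reach steady state, defined as serum concentration exceeding 90% of the final plateau, is about 2 to" "3 days, being at 60% of steady state within at day 1 and 85% at day 2". Section 3.4 repeats the 60% and 85% figures, "respectively at day 1 and 2, and 100% steady state is reached on day 3 from the first day of insulin" degludec injection, and pairs them with the daily pump reductions ("Therefore, 50% and 75% dose reduction proposed in the overlap transition strategy of the first 2" days). No washout figure is given.

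**The concern.** Degludec persists after the last injection, so how well the 24 h half-rate basal protects depends on when that injection was given. The protocol does not fix this. A participant who does exactly as told takes a full dose at home on the Visit 3 morning and then has half of usual pump basal added on top. From 24 h the pump is back at full rate while degludec is still present.

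The call meant to pick up major hypoglycemia comes about a week later. By the protocol's own figure of roughly 3 days to equilibrate, the period of risk has then largely passed. The study sensor has been removed, and a personal real-time CGM is allowed in week 3 but not supplied.

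At stake is participant safety in both arms alike. The step comes after the endpoint week.

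**Working it through.** **Inputs.** Build-up of 60%, 85% and 100% of steady state on days 1, 2 and 3 (background; 3.4). Entry taper for Group 2: pump at 50%, 25% and 0% of usual basal (6.3, Table 2). Exit: pump at 50% for 24 h, then 100% (6.5). Degludec dose 1:1 with pump basal (6.3).

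**Assumptions.** Washout mirrors build-up, so residual degludec = 100 − build-up = 40%, 15% and 0% in successive daily intervals after the last dose's own 24 h. Serum level stands for basal effect, and insulin need is unchanged. The documents state none of these.

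**Formula.** Daily basal load = pump % + degludec %, as a percentage of usual basal. The stepwise version pairs daily levels with daily pump rates, as section 3.4 does.

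| Case | Day 1 | Day 2 | Day 3 | Total |
|---|---|---|---|---|
| Group 2 entry taper | 50+60 = 110 | 25+85 = 110 | 0+100 = 100 | 320 |
| Exit, last dose the morning before Visit 3 | 50+40 = 90 | 100+15 = 115 | 100+0 = 100 | 305 |
| Exit, dose also taken on the Visit 3 morning | 50+100 = 150 | 100+40 = 140 | 100+15 = 115 | 405 |

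The last two rows differ by 405 − 305 = 100 points, one full daily dose, as they should.

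**In units**, for the protocol's 20 units/day example. Without a Visit 3 dose: −2, +3 and 0 units against usual. With one: +10, +8 and +3.

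**Sensitivity.** The loads were also computed with residual degludec falling continuously between the daily figures (linear or piecewise exponential) and Visit 3 falling 0 to 8 h after the usual dosing time (assumed).

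- No Visit 3 dose: about 98-120%, 118-128% and 103-110%.
- Dose on the Visit 3 morning: about 145-150%, 148-170% and 118-128%.

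The upper ends of the first two days are the linear case at 0 h. Without a dose, day 1 is 50 + (100+40)/2 = 120 and day 2 is 100 + (40+15)/2 = 127.5. With a dose, they are 50 + 100 = 150 and 100 + (100+40)/2 = 170.

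The entry taper also changes on this reading. Linear build-up from zero gives 50 + (0+60)/2 = 80, 25 + (60+85)/2 = 97.5 and (85+100)/2 = 92.5. So the statement that exit is no worse in total than entry holds on the stepwise reading of section 3.4 only.

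**Contact gap.** Visit 3 on day 14±1 and the call on day 21±1: nominal 21 − 14 = 7 days, shortest 20 − 15 = 5, longest 22 − 13 = 9. Counted from the end of the 24 h reduced basal, the gap is 4 to 8 days.

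**The case against.** The strongest reply is that the large figures belong to the less likely reading. Visit 3 is labelled end of treatment, pens come back, and mornings 7 to 13 make seven doses for a one-week phase. The half-rate basal also makes most sense if no full dose was taken that day. This stands, and on that reading little is left in the stepwise model. It does not remove the gap: pens are returned at the visit, after a participant may already have injected at home, and the ±1 day windows mean that a dose count cannot define the last dose.

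The visit is also face to face, with glucose data in hand and discretion over basal and bolus doses. Participants have used a pump for at least 6 months, have been trained in treating hypoglycemia, and were excluded for unawareness or recent severe hypoglycemia. They can contact the study team, and may receive instructions in material not visible here. These points reduce the risk, and staff could easily ask about that morning's dose. But the written discretion refers to glucose control during the study, not to the last dose. Section 5.3 promises instructions on stopping study medication safely to those who withdraw; 6.5 has no last-dose counterpart for completers.

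The entry calls are an imperfect comparator, because they also carry Group 2's pump instructions. Their safety checklist does apply to both arms.

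Three stronger readings are tempting and not supported:

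- **The protocol prescribes double basal cover at exit.** It is silent on that dose, and the context points the other way.
- **Participants would be harmed.** The documents link no basal excess to a hypoglycemia rate.
- **A second reduced-basal day is needed.** With the last dose the morning before, the modelled day-2 excess is about 15% stepwise (up to about 28% interpolated). Extending the taper is a clinical preference.

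**Conclusion.** The point holds as a minor, inexpensive safety improvement. Two facts are in the text: no rule covers degludec on the Visit 3 morning, and no contact is scheduled for 5 to 9 days after the pump restarts. The unstated dose moves the modelled first-day load from about 90% to about 150% of usual basal, and the second day from about 115% to about 140%. These sizes rest on mirrored washout, serum level standing for effect and unchanged insulin need; the direction does not depend on the exact figures. On the likelier intent the exit is roughly in line with what the protocol gives Group 2 on entry, read stepwise.

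A reader might infer a threat to the trial's result. There is none: both arms go through the same step, after the endpoint CGM has been removed.

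**What to change.** 1. **Section 6.3 (Visit 2 instructions), repeated at phone call 2 in 6.4:** state that the last degludec dose is the morning before Visit 3 and that none is taken on the day of Visit 3. It belongs here because participants must know before that morning.
2. **Section 6.5:** have staff confirm the time of the last dose before the pump is restarted. If a dose was taken that morning, delay restarting pump basal or reduce it further, at the investigator's discretion.
3. **Section 6.6 and Table 4:** add one short safety call by existing staff about 24 h after Visit 3, when the temporary basal ends. Keep the day 21 call.

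The cost is a few sentences, one Table 4 entry and about 30 short calls (one per completer). No visit, participant or analysis is added.

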163 We hypothesize that, as compared to the actual standard of care transition strategy (1:1 dose
164 conversion at the day of CSII to MDI transition), an alternative transition strategy will result in
165 lower time spent in hyperglycemia without increasing the risk for hypoglycemia. The alternative
166 strategy being (overlap transition strategy):

- 167 • Administration of insulin degludec at a 1:1 basal dose conversion dosage at day 0, with the
168 concomitant use of the insulin pump for 48 hours from transition, where CSII basal rate

169 will be reduced by 50% during the first 24 hours from transition and by 75% during 24 to
170 48 hours from transition. CSII will be disconnected after 48 hours from transition.

171 **3.2. Endpoints:**

172 Primary and secondary endpoints will be analyzed from 1-week of blinded CGM use during
173 randomization phase.

174 Primary endpoint:

175 1. Time spent in CGM glucose levels >180mg/dl

176 Secondary endpoints:

177 1. Time spent in CGM-measured “time-in-range”(glucose levels ≥ 70 mg /dl and ≤ 180 mg/dl)

178 2. Time spent in CGM-measured hypoglycemia < 70 mg/dl

179 3. Frequency of severe hypoglycemia as defined by the ADA (severe cognitive impairment
180 requiring external assistance for recovery) and severe hyperglycemia (BG \geq 250 needing
181 hospitalization)

182 4. Number of boluses (correction boluses) between groups during first 72 hours of
183 randomization

[figure not shown]
184 5. Patient-Reported Outcomes (PRO) using validated questionnaires; insulin delivery
185 satisfaction survey (IDSS) and Work Productivity and Activity Impairment Questionnaire:
186 Specific Health Problem V2.0 (WPAI: SHP) [18,19]

187 **3.3. Study design:**

188 • This is a 3-week, randomized control, open label, single center clinical trial with two study
189 arms comparing the efficacy and safety of the ‘standard of care transition’ and an ‘overlap
190 transition’ strategy

- 191 • The study consists of a screening phase, one week of run-in phase (blinded CGM
- 192 monitoring), one week of the experimental protocol following randomization phase and
- 193 one week of follow-up phase.
- 194 • Overall, the study will last 3 weeks that includes four clinical trial phases (**Figure 1**):
- 195 ○ Screening phase (Week 0): After informed consent, inclusion and exclusion, blinded CGM
- 196 will be inserted.
- 197 ○ Run-in phase (Week 0 to end of week 1): Subjects will wear blinded CGM and continue to
- 198 use CSII.

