721 Suspected Unexpected Serious Adverse Reactions (SUSAR)

722 An unexpected adverse reaction (UAR) is an adverse reaction that is not consistent with the

723 product information in the summary of product characteristics (SPC, i.e.US prescribing

724 information). The current version or any updated if available during the clinical trial for US
725 prescribing information for study drugs will be used as SPC. If UAR is severe enough to define as
726 SAE is called as SUSAR.

727 Technical complaint

728 A technical complaint is any written, electronic, or oral communication that alleges product
729 (medicine or device) defects. The technical complaint may be associated with an AE, but does not
730 concern the AE itself.

731 Reportable Device Issues

732 AE and Unexpected Adverse Device Events (UADE) arising from the use of blinded CGM
733 (Dexcom G6) will be reported irrespective of severity, except in following circumstances:

734 The following device issues are anticipated and will not be reported unless the criteria for AE
735 reporting described above are met

- 736 • Component disconnections
- 737 • CGM sensors lasting fewer than 7 days
- 738 • CGM tape adherence issues
- 739 • Battery lifespan deficiency due to inadequate charging or extensive wireless
740 communication
- 741 • Intermittent device component disconnections/communication failures not leading to
742 system replacement
- 743 • Device issues clearly addressed in the user guide manual that do not require additional
744 troubleshooting
- 745 • Skin reactions from CGM sensor placement that don't meet criteria for AE reporting

746

747 **Safety Monitoring Officer**

748 A safety-monitoring officer ([name]) will independently monitor the study, including
749 adverse events and study drug or device issues with potential to impact participant safety. A
750 monthly meeting will be held between study team and the safety officer to review any adverse
751 events. Following each safety review, a summary recommendation from the safety monitoring
752 officer will be collected.

753 Reporting and follow-up of adverse events

754

755 All events meeting the definition of an AE must be collected and reported. This includes events
756 from the first trial-related activity after the subject has signed the informed consent until the end of
757 the post-treatment follow-up period.

758 During each contact, the trained professional research associate will ask the subject about AEs and

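### Adverse events in the follow-up week are recorded but kept out of the analysed safety summary, although the objective includes safety and AE collection runs to the end of follow-up

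*Combined protocol and SAP*

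**What the plan says.** Section 6.6 sets up a phone call at day 21±1 to check for major glucose events. The coordinator is to "assist subjects if they require insulin dose adjustments. AE/ SAE will be recorded, if any", "during third week of clinical trial. However, they would not be a part of statistical analysis".

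Four other places bear on this sentence:

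- **Section 2, objectives:** "The primary objective of this study is to evaluate the efficacy and safety of an alternative CSII to" MDI transition strategy. Safety stands beside efficacy in the primary objective.
- **Section 6.8, safety assessments:** AE/SAE and documented hypoglycemic episodes are listed, with no limit to the randomized week.
- **Section 14, reporting and follow-up of adverse events:** the collection period runs "from the first trial-related activity after the subject has signed the informed consent until the end of" post-treatment follow-up.
- **Section 6.5, Visit 3:** "Subjects will be transitioned back to their preclinical trial insulin pump regimen. The same" settings apply unless the investigator changes them. To lower the risk of "hypoglycemia, subjects will be advised to set a 50% temporary basal insulin rate for 24 hrs" after degludec.

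Section 3.2 limits the endpoints separately: "Primary and secondary endpoints will be analyzed from 1-week of blinded CGM use during" the randomization phase. Secondary endpoint 3, the frequency of severe hypoglycemia and severe hyperglycemia, falls under that limit. Section 8.2 describes no analysis of general AEs for any week.

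**The concern.** The plan collects week-3 events for safety reasons and then rules them out of the analysis without explanation. Week 3 is not a neutral washout. It begins with a switch from an insulin that the background section calls ultra-long acting to a pump, and the protocol itself attaches a hypoglycemia precaution to that switch. Some events in the first days could plausibly follow from study-drug exposure. If the final report follows section 6.6 literally, its safety summary stops at Visit 3, and a reader could take a clean table to cover the whole post-randomization period.

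The question also matters for the intended use. The background section cites temporary breaks from the pump as one reason for studying the transition. For those patients, the return to the pump is part of the same episode of use.

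**Working it through.** The plan gives no figure for this point. Its only design calculation is the power statement in section 8.1. That statement reproduces: a two-sided t-test with 15 per group and effect size 148.4/140 = 1.06 has 80.0% power. Nothing below depends on it, and including week-3 events changes neither the sample size nor the power.

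**1. Share of follow-up time affected.** Sections 6.1 and 6.7 put Visit 2 at day 7, Visit 3 at day 14 and phone call 3 at day 21, each ±1 day.

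- Nominal share: (21 − 14)/(21 − 7) = 7/14 = 50%.
- Smallest share within the windows: (20 − 15)/(20 − 6) = 5/14 = 36%.
- Largest share within the windows: (22 − 13)/(22 − 8) = 9/14 = 64%.

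**2. How much of week 3 could carry residual degludec.** The documents give no washout figure and do not state when the last dose falls relative to Visit 3. Section 1 gives accumulation of 60% of steady state at day 1 and 85% at day 2. Assume that decline after the last dose mirrors accumulation, so that the remaining fraction is 1 minus the accumulated fraction:

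| Time after last dose | Remaining fraction of steady state |
|---|---|
| 24 h | 1 − 0.60 = 40% |
| 48 h | 1 − 0.85 = 15% |
| 72 h | about 6% if the decline stays geometric (0.40³ = 6.4%; 0.15^1.5 = 5.8%); 0% if day 3 is taken as full steady state, as in section 3.4 |

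Under this assumption the overlap of degludec with the resumed pump fills roughly the first two to three days of week 3, not all seven.

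**3. What other scheduled record exists for week 3.** The second blinded sensor is removed and downloaded at Visit 3 (section 6.5). Meter downloads are described at Visits 2 and 3 only. The schedule in section 6.7 marks the glucose and insulin diary at Visit 2 and phone calls 1 and 2. Personal real-time sensors are allowed again in week 3 (section 6.1), but no collection of their data is planned. The AE/SAE report at phone call 3 is therefore the main scheduled safety record for the week.

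**4. Test or table?** Assume 15 participants per arm. Fisher's exact two-sided p for 4 versus 0 events is 2·C(15,4)/C(30,4) = 2·1365/27405 = 0.10. For 5 versus 0 it is 2·C(15,5)/C(30,5) = 2·3003/142506 = 0.042. A formal comparison would need at least a 5-to-0 split, so it would say little. A descriptive table is different. The chance that at least one of 30 participants has an event is 1 − (1 − p)^30, which is 45%, 79% and 96% at assumed weekly per-participant rates of 2%, 5% and 10%. These rates are illustrations, not figures from the documents.

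**The case against.** The strongest reply is that exclusion from statistical analysis is not exclusion from safety evaluation. Section 14 requires all AEs to be collected and reported through follow-up, a safety officer reviews them monthly, AEs go to the review board, and SAEs go to the sponsor. A reader might infer from section 6.6 that a severe hypoglycemia after Visit 3 would be lost to safety evaluation. The documents do not support that. This part of the reply stands.

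The reply continues that week 3 lies outside the randomized question. The objective concerns the change from pump to injections, both arms receive degludec at the same conversion, and the return to the pump is described identically for both. The overlap strategy under test is confined to the first 48 hours after randomization, which are analysed. A reader might infer that the exclusion biases the comparison between arms. The documents do not show that. Section 6.5 does let investigators adjust doses according to glucose control during the study, and the trial is open label, so identical week-3 management is not guaranteed. That is a reason to display events by arm, not evidence of bias.

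A third argument is that section 8.2 plans no general AE analysis, so the sentence has little to act on, and that week 3 is less standardised. Both observations are fair. The first leaves section 6.6 as the only statement of how AEs enter the analysis, and that statement is an exclusion. The second is a reason to show the follow-up week separately, not to omit it.

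Finally, a reader might take all seven excluded days to be degludec overlap. Step 2 of the working points to the first few days only.

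**Conclusion.** The point holds as a modest correction to the safety reporting. Section 6.6 contains an explicit, unexplained exclusion that sits poorly with the objective, section 6.8 and section 14. It keeps post-exposure events out of the trial's analysed safety summary for 7 of the nominal 14 post-randomization days (36% to 64% of the time at the limits of the visit windows). The days that matter most are probably the first two or three. That estimate rests on the assumption that degludec declines as it accumulates, since the documents give no washout figure.

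The primary and secondary endpoints, the sample size and the between-arm efficacy comparison are unaffected. Oversight of individual cases is intact. What is incomplete is the analysed safety summary.

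**What to change.** Replace the exclusion sentence in section 6.6, and add a matching line to section 8.2, to this effect: all AEs and SAEs, including severe hypoglycemia and severe hyperglycemia, will be tabulated descriptively by randomized arm from the first degludec dose to phone call 3, with the randomized week and the follow-up week in separate columns and no formal test. Keep secondary endpoint 3 on the randomized week, and label the second column as follow-up after the return to the pump. This brings section 6.6 into line with sections 6.8 and 14.

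The cost is one extra column of data that are already collected. The downside is that the column describes a less standardised period, which the label should make plain. The change requires no alteration to visits, treatment or sample size.
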